9.1.1.3. Matching process

As in prior applications of observational studies of the Pfizer-BioNTech COVID-19 using an unexposed comparator,²¹⁻²⁴ the cohort study will match exposed to unexposed individuals using a 1:1 ratio. Matching will be done with replacement, as follows.

- On the day an exposed individual receives a bivalent vaccine dose, individuals will be matched to unexposed individuals who, on that same day, have exactly the same values for the matching variables, provided that both members of the pair meet the eligibility criteria that day. If more than one unexposed individual is found to match a bivalent vaccinated individual, one will be selected at random.
- Exposed individuals will be allowed to have served as unexposed controls in prior matches, and unvaccinated individuals will be allowed to serve as controls more than once (during different time periods).

Individuals will be matched on the following variables, that have been shown to control for confounding well in prior studies:^{21,22}

- Age – 2-year age groups (consecutive years);
- Sex (male, female) – exact matching;
- Place of residence – exact matching, at the level of clinical practice, neighbourhood, or proxy as available (specific for data source);
- History of COVID-19 vaccination, containing the following categories – exact matching:
 - Never vaccinated;
 - Vaccinated with a total of i doses (where i can range from 1 to the maximum number of plausible doses at the time the matching is performed) with the last dose received in calendar month j (where j can range from the first month to the last month of the study period);
- Brand of last COVID-19 vaccine received;
- History of hospitalisation for COVID-19;
- Pregnancy status yes, no (exact matching):
 - Among pregnant women, matching will take a ‘greedy matching’ approach, in which a matched individual will be sought first by last menstrual period (LMP) within 7 days of each other; if no matches are found, the matching period will be extended to 30 days;
- Immunocompromised (yes/no) – exact matching;
- Number of pre-existing conditions considered by the Centers for Disease Control and Prevention (CDC) as risk criteria (0, 1, >1);²²
- Socioeconomic status/education level (as available, exact matching);
- This selection of matching variables is based on prior observational studies.^{22,24,25} The selection of variables will be tailored based on the availability of variables in each data source.

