9.2.2. Exclusion criteria

Individuals who have had a diagnosis of the specific AESI being analysed within one year before time zero (to differentiate the recording of previous events from true new events) and at any time before time zero for diabetes type 1 will be excluded from the cohort and SCRI designs.

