9.3.2. Outcomes

The list of AESIs to be analysed as outcomes and the preferred study design are based on those proposed by the EMA -sponsored ACCESS project (vACCine COVID-19 monitoring readinESS) and also, for consistency, those included in the ongoing PASS of the Pfizer BioNTech COVID-19 monovalent vaccine (EUPAS41623). The AESIs are listed in Table 1 by body system, with the corresponding risk interval and preferred study design (Section 9.1). Clinical validation will be considered for specific AESIs.

Table 1. Safety outcomes: adverse events of special interest (AESIs) with estimated risk intervals and preferred study design

Body system / classification	Adverse event of special interest	Estimated risk interval (days)*	Preferred study design*
Autoimmune diseases	Guillain-Barré syndrome ^a	42	Cohort/SCRI
	Acute disseminated encephalomyelitis	42	Cohort/SCRI
	Narcolepsy ^a	42	Cohort/SCRI
	Acute aseptic arthritis	42	Cohort/SCRI
	Diabetes mellitus type 1	365	Cohort
	(Idiopathic) thrombocytopenia ^a	42 ^a	Cohort/SCRI
	Thrombosis thrombocytopenia syndrome (TTS) ^a	15 ^a	Cohort/SCRI
	Myositis	365	Cohort
Cardiovascular system	Acute cardiovascular injury including microangiopathy	365	Cohort
	Arrhythmia	365	Cohort
	Heart failure	365	Cohort
	Stress cardiomyopathy	365	Cohort
	Coronary artery disease	365	Cohort
	Myocarditis or pericarditis ^a	7; 14; 21	Cohort/SCRI
	Myocarditis ^a	7; 14; 21	Cohort/SCRI
	Pericarditis ^a	7; 14; 21	Cohort/SCRI
Circulatory system	Coagulation disorders: thromboembolism, haemorrhage	28	Cohort/SCRI

PFIZER CONFIDENTIAL

CT24-WI-GL02-RF02 4.0 Non-Interventional Study Protocol Template For Secondary Data Collection Study

01-Jun-2022

Page 23 of 64

090177e19fa902a7Approved\Approved On: 12-Jan-2024 21:20 (GMT)

Table 1. Safety outcomes: adverse events of special interest (AESIs) with estimated risk intervals and preferred study design

Body system / classification	Adverse event of special interest	Estimated risk interval (days)*	Preferred study design*
	Single organ cutaneous vasculitis	28	Cohort/SCRI
	Cerebral venous sinus thrombosis	28 ²⁸	Cohort/SCRI
Hepato-gastrointestinal and renal system	Acute liver injury	365	Cohort
	Acute kidney injury	365	Cohort
	Acute pancreatitis	365	Cohort
	Rhabdomyolysis	365	Cohort
	Glomerulonephritis	365	Cohort
Nerves and central nervous system	Generalised convulsion	42	Cohort/SCRI
	Meningoencephalitis	42	Cohort/SCRI
	Transverse myelitis ^a	42	Cohort/SCRI
	Bell's palsy	42	Cohort/SCRI

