Respiratory system	Acute respiratory distress syndrome	365	Cohort
Reproductive system	Secondary amenorrhea	183	Cohort
	Hypermenorrhea	183	Cohort
Skin and mucous membrane, bone and joints	Erythema multiforme	42	Cohort
	Chilblain-like lesions	42	Cohort
Other	Anosmia, ageusia	42	Cohort
	Anaphylaxis ^a	1 ³¹	Cohort/SCRI
	Multisystem inflammatory syndrome	42	Cohort
	Death (any causes)	365	Cohort
	Subacute thyroiditis	365	Cohort
	Sudden death	365	Cohort
Pregnancy outcome, maternal	Gestational diabetes	Any time pregnancy	Sub-cohort
	Preeclampsia	After 20 weeks gestation	Sub-cohort
	Maternal death	Any time pregnancy	Sub-cohort
Pregnancy outcome, neonates. Define design taking trimester into account	Foetal growth restriction	Any time pregnancy	Sub-cohort
	Spontaneous abortions	At spontaneous abortion	Sub-cohort
	Stillbirth	At birth	Sub-cohort
	Preterm birth	At preterm birth	Sub-cohort
	Major congenital anomalies ^a	1 year after birth	Sub-cohort
	Microcephaly	At birth	Sub-cohort
	Neonatal death	At birth	Sub-cohort
Termination of pregnancy for foetal anomaly	At termination	Sub-cohort	

090177e19fa902a7Approved\Approved On: 12-Jan-2024 21:20 (GMT)

Table 1. Safety outcomes: adverse events of special interest (AESIs) with estimated risk intervals and preferred study design

Body system / classification	Adverse event of special interest	Estimated risk interval (days)*	Preferred study design*
	Small size for gestational age	Any time pregnancy	Sub-cohort
Any	Severe COVID-19 ^b	Any	Cohort

SCRI = self-controlled risk interval

* Time zero corresponds to the day of vaccination (i.e., a 42-day risk interval means that individuals are followed from the day of vaccination to day 41). Risk interval based on the ACCESS project results and other publications.

a For these AESI clinical validation will occur.

b Severe COVID-19 defined as either COVID-19 hospitalisation or death

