9.3.3.4. Comorbidities

- History of anaphylaxis;
- History of allergies;
- Diabetes mellitus (types 1 and 2);
- Hypertension;
- Cardiovascular disease;
- Cerebrovascular disease;
- Chronic respiratory disease;
- Chronic kidney disease;
- Chronic liver disease;
- Cancer;
- Autoimmune disorders;
- Influenza infection or other respiratory infections;
- Charlson Comorbidity Index (CCI scales will be reported and additionally CCI component morbidities will be reported).
- CDC at risk groups

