9.3.3.9. Surrogates of frailty

The following variables will be used as surrogates of frailty (as available):

- Paralysis;
- Parkinson's disease;
- Skin ulcer;
- Weakness;
- Stroke/brain injury;
- Ambulance transport;
- Dementia;
- Difficulty walking;
- Psychiatric illness;
- Sepsis;
- Heart failure;
- Podiatric care;
- Bladder incontinence;
- Diabetes complications;

- Arthritis;
- Coagulation deficiencies;
- Vertigo;
- Lipid abnormalities.

The CDC at risk groups will be defined based on at-risk medical conditions for developing severe COVID-19 and will be reported as baseline characteristics for vaccinated and non-vaccinated individuals. These will be defined based on scientific evidence available on the US Centers for Disease Control and Prevention website and the UK National Health Services digital website. Those websites are updated regularly and provide a classification based on levels of evidence.

At-risk medical conditions that are considered as at higher risk to develop severe COVID-19 are summarised in [Table 2](#). Medicinal products that can be considered as proxies for these conditions are also listed. At-risk subgroups will be identified using medical codes and associated dates for at-risk medical conditions characterising at-risk groups for developing severe COVID-19 as well as prescription and/or dispensing records for drug exposures which may be used as proxies for their identification. At-risk subgroups will be created for each of the at-risk medical conditions listed in [Table 2](#). Multimorbidity, ie, individuals in more than one at-risk subgroup, will be included in each subgroup.

Table 2. Comorbidities and related medicinal products with evidence of being at high risk for developing severe COVID-19

At-risk medical conditions identified by diagnosis codes	Medicinal product proxy(ies) (ATC code)
Cancer (with chemo/immuno/radiotherapy, cancer treatment, immunosuppressant; targeted cancer treatment (such as protein kinase inhibitors or PARP inhibitors); blood or bone marrow cancer (such as leukaemia, lymphoma, myeloma))	Alkylating agents (L01A) Antimetabolites (L01B) Plant alkaloids and other natural products (L01C) Cytotoxic antibiotics and related substances (L01D) Other antineoplastic agents (L01X) Hormones and related agents (L02A) Hormone antagonists and related agents (L02B) Immunostimulants (L03) Immunosuppressants (L04)
Type 1& 2 Diabetes	Blood glucose lowering drugs A10A & A10B

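### The type 1 diabetes exclusion looks only for an earlier type 1 diagnosis, so people with other known diabetes stay at risk and may be counted as new cases unless the event algorithm screens them out

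*Protocol*

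**What the plan says.** Section 9.2.2 sets one general exclusion, "Individuals who have had a diagnosis of the specific AESI being analysed within one year before time zero", and one exception: people with the diagnosis "at any time before time zero for diabetes type 1 will be excluded from the cohort and SCRI designs". Its stated purpose is to separate re-recorded old events from genuinely new ones.

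Other places in the protocol that bear on this:

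- **Table 1 (Section 9.3.2)** lists "Diabetes mellitus type 1" with a 365-day risk interval, cohort design only. It lacks the footnote mark that reads "For these AESI clinical validation will occur". "Gestational diabetes" is also listed, also without the mark.
- **Section 9.3.3.4** lists diabetes of types 1 and 2 as a baseline comorbidity. **Table 2** defines a diabetes at-risk group by diagnosis codes, with "Blood glucose lowering drugs A10A & A10B" as the drug proxy.
- **Section 9.1.1.3** matches on a count of CDC risk conditions (0, 1, more than 1), not on diabetes itself. **Section 9.7.1.6** adds inverse probability weights built from the Section 9.3.3 covariates.
- **Section 9.6, Step 2** promises broad and narrow event algorithms that may use medications and may differ by data source. It also promises manual review of a sample of events. The content of the type 1 diabetes algorithm is not given.

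**The concern.** By giving type 1 diabetes an unlimited look-back, the protocol recognises that old diabetes can be recorded as new. The length of the look-back is sound; the condition it looks for is too narrow. A person already recorded with type 2 or unspecified diabetes, or already on insulin, passes the exclusion. If a type 1 code first appears within 365 days, it may be existing diabetes relabelled rather than a new onset.

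Such events would have nothing to do with vaccination. New-onset type 1 diabetes is a rare outcome, so even a low relabelling rate in a common condition could add a noticeable share of false events. Weighting can balance diabetes between arms, but it cannot remove false events from either. Because the outcome is cohort-only, there is no self-controlled analysis to set against it.

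**Working it through.** **The plan's own figure.** Table 3 gives, for 1,000,000 per group, an unvaccinated risk of 1 per 50,000 and a risk ratio (RR) of 2, a 95% interval of 1.17 to 3.42. Expected events are a = 40 exposed and b = 20 unexposed. With SE = √(1/a − 1/n + 1/b − 1/n) = 0.274, the limits are 2 × exp(±1.96 × 0.274) = 1.17 and 3.42. The other rows of Table 3 reproduce in the same way. The protocol gives no figure for type 1 diabetes itself, so everything below adds assumptions.

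**Adding false events.** Let I be the true one-year risk in the unexposed group, d1 and d0 the share with other known diabetes in the exposed and unexposed, and m the one-year risk of a first type 1 code among them. Then

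observed RR = (RR × I + d1 × m) / (I + d0 × m).

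Take n = 1,000,000 per group, true RR 2 and, as an assumption, d1 = d0 = 10%:

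| m (assumed) | False events per group | Events, I = 1 per 50,000 | Observed RR (95% CI) | Observed RR, I = 1 per 5000 |
|---|---|---|---|---|
| 0 | 0 | 40 v 20 | 2.00 (1.17 to 3.42) | 2.00 |
| 0.01% | 10 | 50 v 30 | 1.67 (1.06 to 2.62) | 1.95 |
| 0.1% | 100 | 140 v 120 | 1.17 (0.91 to 1.49) | 1.67 |
| 0.5% | 500 | 540 v 520 | 1.04 (0.92 to 1.17) | 1.29 |

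Over I = 1 to 20 per 100,000, d = 5% to 15% and m = 0.01% to 0.5%, a true RR of 2 shows as 1.01 to 1.98. With d1 = d0, a true RR of 1 stays at 1.

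**Unequal diabetes, before weighting.** Take I = 1 per 50,000, m = 0.1% and true RR 1, counting per 100,000:

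- 12% v 10%: (2 + 12)/(2 + 10) = 1.17
- 15% v 10%: 17/12 = 1.42
- 8% v 10%: 10/12 = 0.83

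**A second set of assumptions**, with incidence applied only to people without diabetes: 15 per 100,000 per year, 15% with other diabetes, 0.1% relabelled. True events are 15 × 0.85 = 12.75 and false events 15.0 per 100,000, so 15/27.75 = 54% are false. A true RR of 2 shows as (25.5 + 15)/27.75 = 1.46.

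- Milder inputs (25 per 100,000, 10%, 0.05%): (45 + 5)/27.5 = 1.82, with 18% false.
- Harsher inputs (8 per 100,000, 25%, 0.3%): (12 + 75)/81 = 1.07, with 93% false.

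**Risk difference.** Equal false events cancel. In the table's 0.1% row the difference stays at 140 − 120 = 20 per million. Its 95% half-width grows from 1.96 × √60 = 15.2 to 1.96 × √260 = 31.6 per million. In the second set the difference is 40.5 − 27.75 = 12.75 per 100,000, against 15 in people without diabetes.

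**The case against.** The strongest reply is that nothing in the protocol says a type 1 code in a person with known type 2 diabetes is an event. Section 9.6 leaves that to algorithms that may use medications. A narrow algorithm could require no earlier type 2 code or treatment. Such detail properly belongs in the SAP and code lists. This stands, and it makes the point conditional. It does not remove it: Section 9.2.2 already states an eligibility rule for this outcome by name, and that rule is narrower than its purpose. Algorithms may also differ by data source, so any protection could differ between the estimates pooled under Section 9.7.1.9.

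The documents do not support four stronger readings:

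- **That no record check could catch these events**, because the validation mark is missing. Section 9.6 plans review of a sample of events, and Section 9.6.3 benchmarks incidence over time, between sources and against published rates. A large excess of false events could show up there. These steps detect a problem; they do not remove each event.
- **That the bias always runs toward 1.** This needs a true effect and similar false-event risk in both arms. Diabetes is not a matching variable, so the unweighted estimate can move either way. If weighting balances diabetes, dilution remains.
- **That the estimate is known to be badly diluted.** Prevalence and relabelling rate are assumptions, and the milder values do little harm. The risk difference, which Section 9.7.1.4 also reports, keeps its value or nearly so.
- **That the self-controlled analysis is affected**, because the sentence mentions it. Table 1 makes this outcome cohort-only.

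**Conclusion.** The point holds in conditional form. As written, Section 9.2.2 leaves people with other known diabetes, or with glucose-lowering drug records, at risk for the type 1 diabetes outcome. Unless the algorithm screens them out, relabelled diabetes can enter as new onset.

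The effect on the risk ratio could be negligible or almost complete dilution (1.98 down to 1.01 for a true value of 2), and the protocol cannot narrow that range. The risk difference is much less affected in value, though false events widen its interval.

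This is an inexpensive improvement to a stated rule, not a demonstrated error in the estimate. Gestational diabetes is a secondary point of the same kind: only an earlier gestational diagnosis within a year excludes, so women with diabetes before the pregnancy remain in the analysis. No size is claimed for it. It rests on the ordinary meaning of the term, which the protocol does not define.

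**What to change.** In Section 9.2.2, for the type 1 diabetes outcome, exclude anyone with any diabetes diagnosis (type 1, type 2 or unspecified) or any A10A/A10B record at any time before time zero. Report the present type 1-only exclusion as a sensitivity analysis. For gestational diabetes, exclude women with diabetes recorded before the pregnancy.

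The Table 2 diabetes variable supplies most of what is needed. Its label names types 1 and 2, so confirm that unspecified diabetes codes are included. If the event algorithms already screen for earlier diabetes in every data source, a sentence in Section 9.2.2 saying so would settle the main point.

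The cost is one or two sentences and one extra analysis. A few true type 1 cases first coded as another type before time zero would be lost, as would people given these drugs for other reasons. The rule is the same in both arms, and the sensitivity analysis shows what it changes.

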9.2.3. Study period

For both study designs, the study period will start on the date of launch of the bivalent BA.1 vaccine in each participating country, (ie, September 2022, at the earliest), since this was the first bivalent vaccine to receive authorisation in the EU, and will end on 31 August 2024 or the date of the latest data availability. Additional follow-up for accrual of data for major congenital anomalies will be included up to 30 June 2025 or the date of the latest data availability (see Figure 2).

Figure 2. Study and follow-up periods

*Exact date will depend on date of authorisation of new Pfizer-BioNTech COVID-19 vaccine

9.3. Variables

9.3.1. Exposure

The exposure categories will be as follows (see [Section 9.1.1.2](#) for definition of time zero):

- **Exposed group:** received a dose of the bivalent BA.1 or bivalent BA.4-5 vaccine. During follow-up, individuals can receive Pfizer vaccines as recommended.
- **Unexposed group:** did not receive any dose of the bivalent BA.1 or bivalent BA.4-5 vaccine at time zero and do not receive any COVID-19 vaccine during the study follow-up.

090177e19fa902a7Approved\Approved On: 12-Jan-2024 21:20 (GMT)

Exposure status will be assessed from recorded prescriptions, dispensing, or administration data for bivalent BA.1 or bivalent BA.4-5. The type of vaccine received and date of vaccination should be obtained from all possible sources that capture COVID-19 vaccination, such as pharmacy dispensing records, general practice records, immunisation registers, vaccination records, medical records, or other secondary data sources. Depending on the data source, vaccines may be identified via nationally used product codes where possible.

If the contributing database cannot differentiate between the monovalent, bivalent BA.1, and bivalent BA.4-5 vaccines, a proxy for vaccine identification will be used (eg, the date of each vaccine introduction in the country, or the date when it is expected that the bivalent BA.1 and bivalent BA.4-5 are mostly used).

Each contributing data source will identify vaccination as follows:

Pedianet (IT) Information on COVID-19 vaccination will include date of administration, type of vaccine, and dose. This information will be collected by the paediatrician at each contact with the individual.

PHARMO (NL): Data on vaccination will be obtained from PHARMO's General Practitioner (GP) database. Information on vaccines includes Anatomical Therapeutic Chemical (ATC) code, brand, and date of administration.

Norwegian health registers, NHR (NO): The national, electronic immunisation register (SYSVAK) records an individual's vaccination status and vaccination coverage in Norway. All vaccinations, including COVID-19 vaccinations are notified to SYSVAK without requiring participant consent. In SYSVAK, the following data are registered: individual personal identifier, vaccine name and ATC code, date of vaccination, reason for vaccination ie, health care professional versus risk-group individual, and the centre where the vaccine was administered.

EpiChron – Aragon data sources (ES): The Aragon Health System (Aragon, Spain) has implemented a specific vaccination register embedded in the electronic health record (EHR) system. COVID-19 vaccination is systematically registered in this register by health care professionals. This register will contain all the relevant information regarding the vaccination process, such as individual's identifier; date of administration and due date for next dose, if applicable; centre of administration; part of the body where vaccine was administered; name of the vaccine; brand (laboratory); dose; and vaccination criterion (risk group to which the person belongs). There is also a free-text section in which health care professionals can include their observations (eg, presence or not of an allergic reaction).

SIDIAP (ES): SIDIAP will have information available on COVID-19 vaccine administration to individuals linked to a unique and anonymous identifier for all 8 million individuals under the Catalan Institute of Health–Primary Care teams. The information will come from the electronic medical records. For each individual, SIDIAP will have date and centre of administration; dose, brand; reasons for vaccination (eg, risk of group); and other information related to vaccination.

PFIZER CONFIDENTIAL

Clinical Practice Research Datalink, CPRD (UK): CPRD contains information recorded by National Health Service (NHS) primary care general practitioners. Information on the administration of COVID-19 vaccines will be available. This will include an encrypted unique person identifier; the name of the vaccine; manufacturer; dose; administration route; date of administration; and medical observations, events, referrals, test results, and prescribed medications recorded by the GP prior to, on, or after the vaccination date. In addition, person demographic, practice-level, and staff-level information will also be available.

Standard CPRD-linked data sets can also be obtained including Hospital Episode Statistics (HES) data sets covering hospital secondary care (accident & emergency, admitted patient care, inpatient and outpatient), Office for National Statistics (ONS) data sets for death registry information, mother-baby link, and an algorithm-based pregnancy register.

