9.1.1.4. Follow-up

Individuals will be followed from time zero until the end of the study period (31 August 2024, or 30 June 2025 for pregnancy outcomes), the occurrence of the AESI being analysed, death, or disenrollment from the data source, whichever occurs first. Additionally, the

PFIZER CONFIDENTIAL

CT24-WI-GL02-RF02 4.0 Non-Interventional Study Protocol Template For Secondary Data Collection Study

01-Jun-2022

Page 18 of 64

matched pair will be censored when the unexposed individual of the pair receives any COVID-19 vaccine or when the exposed individual in the pair receives a non-Pfizer vaccine.

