9.7.1. Cohort design

9.7.1.1. Exposure assignment and follow-up

The main exposure of interest is in the receipt of at least one dose of the bivalent BA.1 or bivalent BA.4-5 vaccine. Individuals will be assigned to each vaccination category according to their data at time zero, as outlined below:

- **Exposed cohort:** Individuals will be assigned to this cohort when they receive a first dose of the bivalent BA.1 or bivalent BA.4-5 vaccine. Individuals will be censored if they receive a non-Pfizer COVID-19 vaccine during follow-up. For the matched comparative analyses individuals will be censored when their matched pair is censored.
- **Unexposed cohort:** Individuals will be assigned to this cohort if they have not received a COVID-19 vaccine at time zero. Individuals will be censored if and when

PFIZER CONFIDENTIAL

they receive a dose of any COVID-19 vaccine during follow-up. Time zero in the unexposed cohort will be the same day when they did not receive a Pfizer-BioNTech COVID-19 vaccine dose. This day will be chosen by calendar matching to the time zero of the corresponding exposed group.

Individuals will be followed from time zero (see [Section 9.1.1.4](#)) until the censoring described above, death, administrative end of follow-up, or end of study period 31 August 2024, whichever occurs first, with pregnancies followed until 30 June 2025 (see [Section 9.7.1.7](#)). For analyses of AESIs with known risk intervals, follow-up will be truncated at the end of the risk interval.

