9.7.1.4. Crude outcome measures

For safety outcomes with a known short risk interval ([Table 1](#)) (e.g., anaphylaxis), the risk (number of events/number of individuals in a cohort) and the corresponding 95% CIs will be computed. Effect estimates will be calculated both as risk differences and as risk ratios, with their corresponding 95% CIs, for those exposed to a Pfizer-BioNTech COVID-19 bivalent vaccine compared with the unexposed group that did not receive any COVID-19 vaccine during follow-up.

For safety outcomes with unknown risk intervals or those that require long follow-up (eg, death), the cumulative incidence will be computed, which will be estimated using the 1 – Kaplan-Meier estimator. Time to outcome will be defined as the time from the baseline date (time zero) until the occurrence of the outcome or censoring (Section 9.1.1.4 and Section 9.7.1.7). The variance will be computed using approaches that account for autocorrelation (eg, the robust estimator or via bootstrapping).^{39,40} Risk differences and risk ratios (and their corresponding 95% CIs) will be estimated at different time intervals, which will be adapted to the specific nature of each outcome.

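### Section 9.3.1 makes staying unvaccinated during follow-up a condition of being a control, which conflicts with time-zero assignment and pair censoring elsewhere; programmed literally, it would bias risk ratios downward

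*Protocol*

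**What the plan says.** Section 9.3.1 lists the exposure categories. A member of the unexposed group is someone who "did not receive any dose of the bivalent BA.1 or bivalent BA.4-5 vaccine at time zero and do not receive any COVID-19 vaccine during the" follow-up period: one condition at time zero and one over the period after it.

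The sections that say how the cohort is built and analysed use a different rule:

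- 9.1.1.2 fixes exposure status at time zero.
- 9.7.1.1: "Individuals will be assigned to each vaccination category according to their data at time zero". For the comparator, "Individuals will be assigned to this cohort if they have not received a COVID-19 vaccine at time zero", with censoring if and when "they receive a dose of any COVID-19 vaccine during follow-up".
- 9.1.1.4: the "matched pair will be censored when the unexposed individual of the pair receives any COVID-19 vaccine". Section 9.7.1.8 repeats this and states the assumption behind it.
- 9.1.1.3: "Exposed individuals will be allowed to have served as unexposed controls in prior matches".

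Two other places use wording like that of 9.3.1. Section 9.1.1.1 gives no vaccination during follow-up as one of the two strategies of the per-protocol contrast. Section 9.7.1.4, for outcomes with a known short risk interval, describes effect estimates for the exposed "compared with the unexposed group that did not receive any COVID-19 vaccine during follow-up".

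**The concern.** A per-protocol strategy is carried out by following people from time zero and censoring them when they depart from it. Section 9.3.1 takes the strategy of 9.1.1.1 and makes it a test of who belongs to the group. Under that test, a control vaccinated in month five is not a control censored in month five; that person is not a control at all.

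This selects on the future. A control who dies early has no time left to be vaccinated and stays in the group. A control who survives and is later vaccinated is removed. The control risk rises and the risk ratio falls. The same can happen with a non-fatal event, because 9.1.1.4 ends follow-up at the event under analysis: a case arising before any vaccination always meets the condition, while a later-vaccinated non-case is dropped. In a safety study, a bias toward apparent protection can hide a real excess risk. Aligning assignment, eligibility and follow-up at time zero in 9.1.1.2 is meant to prevent this.

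**Working it through.** **Step 1: can the texts be read as one rule?** Take a person who is unexposed at time zero and receives a COVID-19 vaccine on day 150.

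| Section | Treatment of this person |
|---|---|
| 9.3.1 | Fails "do not receive any COVID-19 vaccine during the study follow-up"; not a member |
| 9.7.1.1 | Member from time zero; censored on day 150 |
| 9.1.1.4, 9.7.1.8 | Pair contributes to day 150, then is censored |
| 9.1.1.3 | May be a control first and an exposed person later |

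One might try to reconcile them by saying that follow-up has already ended at censoring, so nobody is ever vaccinated during it. Section 9.7.1.1 rules this out: it speaks of a control being vaccinated during follow-up and being censored for it. The rules admit different controls.

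**Step 2: size if 9.3.1 were programmed literally.** The protocol gives no figure on this point. Its one numerical planning table (Table 3) does not bear on it. Later uptake, its timing and the death risk are not stated, so all are assumed.

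Inputs: no true effect; a 365-day horizon (the risk interval for death in Table 1); constant yearly hazards L for death and v for later vaccination. The share of controls who would be vaccinated within the year is u = 1 − e^(−v).

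- Died unvaccinated: d = L/(L+v) × (1 − e^(−(L+v)))
- Alive and unvaccinated at one year: s = e^(−(L+v))
- Control risk under 9.3.1: d/(d+s)
- Risk ratio: (1 − e^(−L)) / [d/(d+s)], which for rare death is close to v/(e^v − 1)

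| Later uptake u | v = −ln(1−u) | e^v − 1 | Null risk ratio |
|---|---|---|---|
| 10% | 0.105 | 0.111 | 0.95 |
| 20% | 0.223 | 0.250 | 0.89 |
| 40% | 0.511 | 0.667 | 0.77 |
| 60% | 0.916 | 1.500 | 0.61 |

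**Step 3: sensitivity to the assumptions.**

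- *Death risk* matters little. With the full formula, uptake of 10%, 30%, 50% and 70% gives 0.95, 0.83, 0.70 and 0.52 at a 1% yearly death risk, and 0.95, 0.85, 0.72 and 0.56 at 10%.
- *Timing* matters a good deal. At 50% uptake and 2% death risk, with vaccinations spread evenly over the window, the ratio is 0.93 for days 0–60, 0.81 for days 0–180, 0.67 for days 0–365 and 0.58 for days 180–365.
- *Different underlying risk.* If later vaccinees have 0.5 to 3 times the death hazard of the others, with 30% to 70% later vaccinated evenly over the year, the ratio runs from 0.42 to 0.98 and stays below 1.

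**Step 4: short-interval outcomes.** Section 9.7.1.1 truncates follow-up at the end of a known risk interval. For 42 days, replace v by v × 42/365. Annual uptake of 20%, 40% and 60% gives 0.0257, 0.0588 and 0.1054, and risk ratios of 0.99, 0.97 and 0.95. This treats the event as ending the chance of vaccination within follow-up.

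**Step 5: both rules on the same data.** In a simulation of 4 million pairs with 2% one-year death risk, 50% later uptake and no effect, pair censoring with 1 − Kaplan-Meier gave 2.00% against 2.00%, a ratio of 1.00. Requiring controls to stay unvaccinated gave a control risk of 2.87% and a ratio of 0.70.

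**The case against.** The strongest reply is that 9.3.1 only restates the strategies of 9.1.1.1, where the phrase is proper, and sends the reader to 9.1.1.2, where status is fixed at time zero. Every operational section then censors. If later-vaccinated controls were excluded, the rules for censoring pairs at the control's vaccination would have nothing to act on. This stands, and it settles which analysis is intended. It does not make 9.3.1 correct: that section formally defines exposure, and its wording joins a future condition to membership.

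A reader might infer that the planned death analysis is biased. The documents do not support that. In 9.7.1.4, death is estimated by 1 − Kaplan-Meier, with time running to the outcome or censoring. The phrase in 9.7.1.4 that resembles 9.3.1 sits in the paragraph on short-interval outcomes and echoes the comparator wording of the primary objective; it is a label, not an eligibility rule.

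A reader might also carry the one-year figures over to short-interval outcomes. Truncation at the end of the risk interval, as 9.7.1.1 requires, keeps the effect to the few per cent in step 4.

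It can also be said that a simple edit does not finish the job in 9.7.1.4, because the short-interval risk there is events divided by persons, which cannot use censoring times. That is right, and the fix allows for it.

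**Conclusion.** The contradiction is real and should be removed: 9.3.1 stands against 9.1.1.2, 9.1.1.3, 9.1.1.4, 9.7.1.1 and 9.7.1.8, and taken literally it is the wrong rule. The direction of bias is downward. A ratio below 1 follows when there is no true effect; a truly raised ratio would be pulled toward or past 1. For a rare outcome the factor in step 2 multiplies the true ratio, so at 40% later uptake an assumed true ratio of 1.3 would appear as 1.3 × 0.77 = 1.00.

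The sizes are illustrations of a literal reading. They are not forecasts of this study's results, since uptake and timing among controls are assumed and timing alone moves the one-year ratio from 0.93 to 0.58 at 50% uptake. The 1.00 under censoring holds if censoring at vaccination is non-informative given the matching and adjustment variables, as 9.7.1.8 assumes.

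**What to change.** In 9.3.1, define the unexposed group by status at time zero only. Replace the clause about follow-up with: *later receipt of any COVID-19 vaccine does not affect group membership; it censors the matched pair on that date (Sections 9.1.1.4, 9.7.1.1 and 9.7.1.8)*. The strategy wording in 9.1.1.1 can stay.

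In 9.7.1.4, refer to the matched unexposed group as defined at time zero, with the same pair censoring. Because the short-interval risk is a simple proportion, either state how pair censoring applies to both members within the risk interval or use 1 − Kaplan-Meier there too.

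The cost is a few sentences of protocol text and, for the short-interval outcomes, a small change to the analysis. No further data are needed.
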